**ABBREVIATIONS**

ABBREVIATION	DEFINITION OR DESCRIPTION
5-FU	5-fluorouracil
ADA	Anti-drug antibody
ADR	Adverse drug reaction
AE	Adverse Event
AJCC	American Joint Committee on Cancer
ATC	Anatomical Therapeutic Chemical
AUC	Area under the curve
AUC 0-t	Area under the concentration-time curve from zero up to a time t
AUC 0-∞	Area under the concentration-time curve from zero up to ∞ w
AUC %extrap	Area under the concentration-time curve extrapolated in % of the total AUC
AUC 0-tau	Area under the concentration-time curve from zero up to the last concentration ≥ BLQ
BLQ	Below limit of quantification
AUC	Area under the curve
BMI	Body Mass Index
BO(R)	Best overall response (rates)
BSA	Body surface area
CB(R)	Clinical benefit (rate)
C avr	Average serum concentration
CL	Clearance
C max	Maximum serum concentration
C min	Minimum serum concentration
CR	Complete response
CRF	Case report form
CSR	Clinical Study Report
CT	Computed tomography
CTC	Common Toxicity Criteria
CTCAE	Common Terminology Criteria for Adverse Events
DSMB	Data Safety Monitoring Board
ECG	Electrocardiogram
ECHO	Echocardiogram

ECOG	Eastern Cooperative Oncology Group
eCRF	Electronic case report form
EGFR	Epidermal growth factor receptor
EMA	European Medicines Agency
EORTC	European Oncology Research Trials Committee
EOS	End of study
Fc $\gamma$ R	Fc-gamma receptor
FDA	Food and Drug Administration
HIV	Human immunodeficiency virus
HPV	Human Papilloma Virus
ICH	International Conference on Harmonization
IMP	Investigational medicinal product
IRR	Infusion related reaction
irRC	Immune-related response criteria
ITT	Intention-to-treat
IWRS	Interactive web response system
MedDRA	Medical Dictionary for Regulatory Activities
MRI	Magnetic resonance imaging
MUGA	Multiple gated acquisition scan
NCI	National Cancer Institute
NYHA	New York Heart Association
OR(R)	Objective response (rate)
OS	Overall survival
PD	Progressive disease
PFS	Progression-free survival
PK	Pharmacokinetic
PP	Per-protocol
PR	Partial response
PT	Preferred term
QLQ	Quality of life questionnaire
QoL	Quality of life
QTc	QT-interval for ECG corrected for heart rate
RECIST	Response evaluation criteria in solid tumors
SAE	Serious adverse event
SAF	Safety population

SAP	Statistical Analysis Plan
SCCHN	Squamous cell carcinoma of the head and neck
SD	Stable disease
SOC	System Organ Class
SOP	Standard Operating Procedure
TEAE	Treatment-emergent Adverse Event
$t_{1/2}$	Terminal half-live
$T_{max}$	Time of maximum serum concentration
TTF	Time to treatment failure
UICC	Union for International Cancer Control
ULN	Upper limit of normal
$V_z$	Volume of distribution during terminal phase
$V_{ss}$	Apparent volume of distribution at equilibrium
WHO	World Health Organization

## 1. SYNOPSIS

This Statistical Analysis Plan (SAP) describes the planned analysis and reporting for Glycotope protocol GEXMab52201 (Randomized, controlled, open label, multicenter, phase II study to evaluate the efficacy and safety of CetuGEX™ plus chemotherapy in comparison to cetuximab plus chemotherapy for the treatment of patients with stage III/IV recurrent and/or metastatic squamous cell carcinoma of the head and neck), version 4.0 dated 06-Feb-2015.

This phase II study is being conducted to assess the efficacy, safety, tolerability, pharmacogenomics and pharmacokinetics of CetuGEX™.

The structure and content of this SAP provides sufficient detail to meet the requirements identified by the Food and Drug Administration (FDA), European Medicines Agency (EMA), and International Conference on Harmonization (ICH) of Technical Requirements for Registration of Pharmaceuticals for Human Use: Guidance on Statistical Principles in Clinical Trials (ICH-E9) [1]. All work planned and reported in this SAP will follow internationally accepted guidelines, published by the American Statistical Association [2] and the Royal Statistical Society, for statistical practice [3].

The planned analyses identified in this SAP may be included in clinical study reports (CSRs), regulatory submissions, or future manuscripts. Also, post-hoc exploratory analyses not necessarily identified in this SAP may be performed to further examine study data. Any post-hoc, or unplanned, exploratory analyses performed will be clearly identified as such in the final CSR.

The following documents were reviewed in preparation of this SAP:

- Clinical Research Protocol GEXMab52201 Final Version 4.0 dated 06-Feb-2015
- Electronic Case report forms (eCRFs) for Protocol GEXMab52201 Final Version 4.0, dated 14-May-2015
- ICH Guidance on Statistical Principles for Clinical Trials (E9)
- EORTC QLQ-C30 Scoring Manual and head and neck cancer module QLQ-H&N35 documentation

The reader of this SAP is encouraged to also read the clinical protocol and other identified documents, for details on the planned conduct of this study. Operational aspects related to collection and timing of planned clinical assessments are not repeated in this SAP unless relevant to the planned analyses.

## 2. STUDY OBJECTIVES AND ENDPOINTS

### 2.1 Study Objectives

#### 2.1.1 *Primary Objective*

The primary objective is to evaluate the efficacy of CetuGEX™ for the treatment of patients with stage III/IV recurrent and/or metastatic squamous cell carcinoma of the

head and neck (SCCHN) as compared to cetuximab (both in combination with platinum-based chemotherapy) in terms of progression-free survival (PFS).

### **2.1.2 Secondary Objectives**

The secondary study objectives are:

- To evaluate further efficacy criteria, safety and quality of life (QoL) of patients with stage III/IV recurrent and/or metastatic SCCHN treated with CetuGEX™ as compared to cetuximab (both in combination with platinum-based chemotherapy)
- To assess pharmacokinetic (PK) parameters and profiles of CetuGEX™
- To assess efficacy and safety based on genetic markers for immune response (Fc-gamma receptor [FcγR] allotypes) and biomarkers

## **2.2 Efficacy and Safety Endpoints (Target Variables)**

### **2.2.1 Efficacy Variables**

#### Primary efficacy endpoint

The primary efficacy endpoint is PFS as assessed by the investigator.

PFS is defined as time from randomization until disease progression or death of any cause. Date of disease progression is defined as the date of imaging showing disease progression, as assessed by the investigator according to adapted immune-related RECIST 1.1 (modified irRC) [5]. The PFS time will be censored at the time of the last tumor assessment if the patient is alive and without progression at the last time of observation.

#### Secondary efficacy endpoints

If not otherwise specified, all response related secondary efficacy endpoints will be derived according to the assessments of the investigator (modified irRC) as well as according to the independent centralized reading assessments (modified irRC and RECIST 1.1).

- PFS, as assessed by independent centralized reading
- Best overall response rates by response category (complete response [CR], partial response [PR], stable disease [SD] or progression [PD]) at the end of combination treatment
- Best overall response rates by response category (CR, PR, SD or PD) including maintenance therapy treatment
- Objective response rate (ORR; i.e., CR + PR) at the end of combination treatment
- Objective response rate (ORR; i.e., CR + PR) including maintenance therapy treatment
- Clinical benefit rate (CBR; i.e., CR + PR + SD) at the end of combination treatment

- Clinical benefit rate (CBR; i.e., CR + PR + SD) including maintenance therapy treatment
- Duration of response
- Overall survival (OS) defined as time from randomization until death of any cause
- Time to treatment failure (TTF)
- QoL as assessed by European Oncology Research Trials Committee (EORTC) QoL questionnaires (QLQ) EORTC-QLQ-C30 and EORTC-QLQ-H&N35
- Relationship of stratification factors, p16, epidermal growth factor receptor (EGFR) intensity and FcγRIIIa allotypes to efficacy endpoints

### 2.2.2 *Safety Variables*

The safety endpoints are:

- Incidence of adverse events (AEs) and serious AEs (SAEs), including incidence of target/class-specific side effects (skin reactions, hypomagnesemia, neutropenia, gastrointestinal AEs, liver enzymes increases, conjunctivitis, mucositis)
- Infusion related reactions (IRRs)
- Physical assessments
- Laboratory assessments
- Vital signs
- Electrocardiogram (ECG)
- Relationship of FcγRIIIa and FcγRIIIa-allotypes, occurrence of ADAs and PK parameters to safety endpoints

### 2.2.3 *Pharmacokinetic Variables*

Antibody trough levels and PK profiles of CetuGEX™ will be assessed throughout the study.

The PK samples for determining CetuGEX™ antibody concentrations will only be collected for the first-line treatment. No PK samples will be collected during the single-agent maintenance therapy, unless combination therapy has been prematurely terminated. There are 2 different groups of PK samples being collected during the first-line treatment.

For all patients randomized to CetuGEX™ treatment group for the first-line treatment, blood sampling for PK trough and maximum levels will be performed during Cycles 1, 2, 3 and 4. Blood samples will be collected before and at the end of each infusion on Day 1, 8, and 15 for Cycles 1, 2 and 3. On Cycle 4, blood samples will be collected before and at the end of each infusion but only on Day 1. Since the first dose of Cycle 1 will be split, there will also be blood samples collected before and at the end of the infusion on Day 0 (first infusion day of Cycle 1). Pre-infusion samples should be collected within 30 minutes prior to the start of the infusion. Post-infusion samples should be collected within 10 minutes following the end of the infusion and within 5 minutes would be ideal.

For a subset of patients, additional blood sampling will be collected on first infusion of Cycle 1 and Cycle 4 to gain a more fully PK profile for the first infusions from both of these cycles. The full profile of Cycles 1 and 4 PK blood samples will include pre- and post-infusion blood samples at 5 hour  $\pm$  5 min, 7 hours  $\pm$  15 min (Day 1), 24  $\pm$  1 hour (Day 2), 48  $\pm$  2 hours (Day 3), 72  $\pm$  2 hours (Day 4), and 7 days (168  $\pm$  2 hours; Day 8) after the start of the infusion on Day 1.

#### **2.2.4 Exploratory Variables**

Further exploratory variables include:

- Immunogenicity: incidence of anti-drug antibodies (ADAs)
- Immunological parameters: cytokine levels and immune cell counts
- Fc $\gamma$ RIIa allotypes
- EGFR intensity and EGFR stained cancer cells

### **3. STUDY METHODS**

#### **3.1 Overall Study Design and Plan**

This is a Phase 2, randomized, controlled, multicenter (approximately 40 sites in Europe and the USA) study with first line treatment (6 cycles of 5-FU and cisplatin in combination with CetuGEX™ vs. combination with cetuximab) followed by single-agent maintenance therapy (CetuGEX™ or cetuximab, respectively).

The study will include 3 separate study periods following screening:

##### Combination treatment phase

Eligible patients will be randomized to receive as first line treatment either CetuGEX™ or cetuximab in combination with 5-FU and cisplatin for the maximum duration of 6 cycles. In case of toxicity, the chemotherapy dose can be reduced, discontinued or, if later than the first cycle, switched to carboplatin. If discontinued earlier for any other reason apart from progression, patients will start the maintenance phase at that time.

As soon as at least 10 patients per treatment arm have completed the second cycle of combination therapy, patient safety data will be reviewed by an independent data safety monitoring board (DSMB).

##### Single-agent maintenance phase

After completion or discontinuation of combination chemotherapy for any other reason than progression, the treatment will be followed by maintenance therapy with CetuGEX™ alone or cetuximab alone, respectively. Single-agent maintenance therapy will be continued until progression of disease or limiting toxicity.

##### Follow-up

A Safety Visit must be performed 28 (+2) days after the last administration of the study drug for all randomized patients. In case of treatment discontinuation due to reasons other

than disease progression, patients will stay on the regular study schedule until disease progression is documented and will then attend a Final Examination Visit. In case of treatment discontinuation due to disease progression, the Safety Visit is identical to the Final Examination Visit.

After the Final Examination, patients will be followed-up by quarterly phone calls until death or for a maximum duration of 24 months after randomization of the last patient for assessment of overall survival.

### **3.2 Selection of Study Population**

Patients aged at least 18 years at screening with stage III/IV recurrent and/or metastatic SCCHN will be enrolled. Inclusion and exclusion criteria are given in sections 8.2.1 and 8.2.2 of the protocol.

### **3.3 Method of Treatment Assignment and Randomization**

Patients eligible for study participation will be randomized using a 1:1 ratio to either the CetuGEX™ or cetuximab arm. Randomization will be stratified by:

- FcγRIIIa status (FF or FV or VV)
- Oral cavity and oropharynx vs. other locations
- Locally recurrent vs. metastatic disease
- EGFR treatment naïve vs. EGFR treatment as part of multimodal therapy

A centralized randomization procedure, the interactive web response system (IWRS), will be used to assign a unique randomization number to each patient.

### **3.4 Treatment Masking (Blinding)**

Blinding at the level of study treatment does not apply since the study is open label.

## **4. ANALYSES AND REPORTING**

### **4.1 Interim Analyses**

No formal interim analysis will be performed. An independent DSMB will periodically review the relevant safety data and provide advice on the continuation, modification or termination of the study. The DSMB will be comprised of 3 members, 2 of them being oncologists and one of them statistician. A study specific charter will define in detail the composition, responsibilities and procedures of the DSMB.

As soon as at least 10 patients per treatment arm have completed the second cycle of first line treatment, a first meeting of DSMB will be scheduled to review the patient safety data. After this meeting, regular 6-monthly meetings will be scheduled until all ongoing patients have been treated for at least 6 months. Starting at the second DSMB meeting, in addition to review of patient safety data a descriptive analysis on progression and survival, including point estimates and 95% confidence intervals of the hazard ratios, will be included to monitor a potential detrimental effect of the investigational compound. For

important reasons additional meetings may be scheduled by the coordinating investigator, sponsor, medical monitor or DSMB members as long as patients are at risk.

#### **4.2 Final Analysis**

No database may be locked or analyses completed until this SAP has been approved.

The database cut-off for the statistical analysis will be set to not earlier than 12 months after randomization of the last patient.

The efficacy analysis will be performed for all patients, regarding the patients still under observation as censored and applying the same rules as defined for missing assessments and loss to follow-up.

At this time, the safety analysis will be performed on all available data, including patients still under treatment.

All statistical results will be made available to Glycotope following database cut-off and compiled into the CSR. Final results associated with OS will be added to the CSR after completion of follow-up for OS which is planned for 24 months after the last patient has been randomized.

Any post-hoc, exploratory analyses completed to support planned study analyses, which were not identified in this SAP, will be documented and reported in appendices to the CSR. Any results from these unplanned analyses (post-hoc) will also be clearly identified in the text of the CSR.

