13 STATISTICS

This section presents a summary of the planned statistical analyses. A statistical analysis plan (SAP) describing in detail the analyses to be conducted will be prepared as a separate document.

The main statistical analysis will be performed when 192 PFS events have been observed. Based on the statistical assumptions as described in Section 13.2 this is expected to occur after 36 months of study duration (24 months recruitment + 12 months follow up). The result of a prolonged follow-up for OS will be analyzed and reported in an amendment to the main analysis.

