13.4.3.2 Secondary Analyses

A Chi-squared test will be performed to evaluate the effects of treatment on response rates as defined in Section 13.1.2. A logistic regression model will be fit to estimate odds ratios for the association of stratification factors, the p16 status, and the EGFR status with response categories. Corresponding 95%-confidence intervals will be calculated for the treatment differences in response rates.

Overall survival and TTF will be analyzed analogously to PFS on an ITT basis. Additional models will be applied to evaluate the impact of second line treatments on OS. Details will be given in the SAP.

If subgroup sample sizes allow, analyses of the primary and secondary efficacy endpoints will be repeated for the FcγRIIIa-allotype subgroups (i.e., FF, FV, VV), the p16 status subgroups as well as the EGFR status subgroups, omitting the FcγRIIIa factor, the p16 status and the EGFR status factor, respectively.

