14.5.1 Regular Study Termination

The end of this study is defined as the date when:

- The number of PFS events required for analysis are reached,
- all patients have discontinued medication, and
- a relevant number of deaths have occurred to obtain information on overall survival.

Within 90 days of the end of the clinical study, Glycotope GmbH or designee will notify the IEC/IRBs and regulatory authorities on the regular termination of the study as required according to national laws and regulations.

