### 9.1 Primary Efficacy Analysis

The primary efficacy analysis for PFS as assessed by the investigator will be based on the ITT population using the PFSp definition as described in Section 7.2.

A two-sided log-rank test will be used to test the null hypothesis of equal treatment effects at an overall significance level of 0.05. The Kaplan-Meier method will be used to estimate the survival functions. Median survival times together with their 95%-confidence intervals will be retrieved from the survival functions. PFS rates at 6, 12, 15 and 18 months and associated 95%-confidence intervals and graphs of the Kaplan-Meier curves by treatment arm will also be presented.

The primary efficacy analysis will not be stratified by the factors used for stratification at randomization in order to preserve the estimated power considering the high number of strata.

To investigate the influence of the stratification factor on the primary endpoint a Cox regression model will be applied as a sensitivity analysis based on the ITT population. This model will include the treatment effect and the stratification factors

- FcγRIIIa allotypes (FF, FV or VV)
- Oral cavity and oropharynx vs. other locations
- Locally recurrent vs. metastatic disease
- EGFR treatment naïve vs. EGFR treatment as part of multimodal treatment

The hazard ratios, the corresponding 95% confidence intervals and the p-values of the Wald test (using adjustment for ties according to Efron) will be presented for all factors. The Kaplan-Meier analyzes will be repeated separately within the subgroups formed by the stratification factors. Corresponding figures will combine the curves for all treatment group/factor level combinations on one page per factor. Factor levels maybe combined if the sample size per level is  $< 15$ .

Further sensitivity analyses will be done as follows

- The analyses will be repeated using the PFSs definition as described in Section 7.2
- The analyses will be repeated for the PP Population
- It has been recognized that not all sites had strictly applied modified irRC for response assessment. To investigate the influence of deviating response criteria on PFS a log rank test will performed stratifying sites according to strict adherence to modified irRC (yes/no).

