### **9.2.4 Overall Survival**

OS will be analyzed applying a not stratified log rank test and a proportional hazards regression model including the stratification factors in addition to the study treatment factor. Kaplan-Meier estimates will be presented as described in Section 9.1. Survival rates at 12, 18 and 24 months and associated 95%-confidence intervals will be presented.

A further proportional hazards regression model will be applied including the study treatment factor, the stratification factors and a dichotomous variable for second line treatment. This model maybe further modified or supplemented to account for different classes of second line treatments.

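### Overall survival appears to be log-rank tested at the main PFS analysis and again after 24 months of follow-up, and the plan does not say that only one test is inferential

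*SAP*

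**What the plan says.** **First analysis.** SAP 4.2 sets the database cut-off no earlier than 12 months after the last randomization and states: "The efficacy analysis will be performed for all patients, regarding the patients still under observation as censored". All statistical results then go to the sponsor and into the clinical study report (CSR). OS is a secondary efficacy endpoint in SAP 2.2.1, and SAP 9.2.4 says "OS will be analyzed applying a not stratified log rank test and a proportional hazards regression model". SAP 15.1 lists the output as Table 14.2.13.1, a log-rank test with Kaplan-Meier analysis. Nothing in these places defers the OS test.

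**Second analysis.** SAP 4.2 continues: "Final results associated with OS will be added to the CSR after completion of follow-up for OS", planned for 24 months after the last patient is randomized. Protocol 13 agrees: "The result of a prolonged follow-up for OS will be analyzed and reported in an amendment to the main analysis".

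**Level.** The 0.05 is attached to PFS in SAP 9.1: "A two-sided log-rank test will be used to test the null hypothesis of equal treatment effects at an overall significance level of 0.05". For OS the only link is protocol 13.4.3.2: "Overall survival and TTF will be analyzed analogously to PFS on an ITT basis". Protocol 13.4.5 and SAP 4.1 rule out a formal interim analysis, but both are about data shown to the safety board.

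**Length of OS follow-up.** It is capped at 24 months after the last randomization in the protocol synopsis, protocol 7.1.1 and SAP 3.1. It is at least 24 months in protocol 13.2 and SAP 5.

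**The concern.** On this text two OS p-values will exist, about a year apart, from the same test on overlapping data. The plan gives no alpha split, spending function or boundary, and no statement that the earlier p-value is descriptive. The report can then present whichever is below 0.05 as an OS difference, and the chance of at least one false positive exceeds 5%.

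OS matters more than most secondary endpoints here. It has its own assumed hazard ratio, its own event projection (183 deaths), an extra year of follow-up and a separate reporting step.

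**Working it through.** **Inputs**
- 240 patients, 1:1, recruited over 24 months (protocol 13.2, SAP 5). Uniform accrual is assumed.
- PFS medians 5.6 and 8.4 months, 80% power, two-sided 0.05, 192 events (same sections).
- OS control median 10.6 months, hazard ratio 0.67, 183 deaths after 24 months of follow-up (same sections). The ratio is taken as 2/3, so the other median is 15.9 months.
- First OS look at month 24 + 12 = 36, or 42 with the 6-month postponement in SAP 5. Final look at month 24 + 24 = 48.
- Exponential drop-out, 10% at the PFS cut-off. The documents do not say how this carries over to OS, so it is varied below.

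**Step 1: the plan's PFS events.** d = 4(1.960 + 0.842)² / (ln HR)². With HR = 5.6/8.4 this is 191; with 0.67 it is 196. The stated 192 reproduces.

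**Step 2: the plan's OS deaths.** For hazard λ = ln 2 / median and drop-out hazard η, expected deaths per arm by month T are

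120 × λ/(λ+η) × {1 − [e^(−(λ+η)(T−24)) − e^(−(λ+η)T)] / [24(λ+η)]}.

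If 10% of patients are observed to drop out by month 36, the month-48 total is 182. If 10% drop out by month 48, it is 185. Both agree with 183. Setting η = 0.0079 per month gives exactly 183, with 156 deaths at month 36 and 172 at month 42. With the control hazard in both arms (the null), the same η gives 172, 187 and 197 deaths at months 36, 42 and 48.

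**Step 3: error over two looks.** With information fraction t = deaths at first look / deaths at final look, the two log-rank statistics are approximately bivariate normal with correlation √t. The chance of at least one significant result under the null is 1 − P(|Z1| < 1.96 and |Z2| < 1.96).

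| Looks (months) | Assumption | Deaths, first / final | t | Error |
|---|---|---|---|---|
| 36, 48 | Null, η = 0.0079 | 172 / 197 | 0.88 | 6.6% |
| 36, 48 | Null, heavier drop-out (η = 0.0124) | 166 / 188 | 0.88 | 6.6% |
| 36, 48 | Planned OS effect, η = 0.0079 | 156 / 183 | 0.85 | 6.8% |
| 36, 48 | Planned OS effect, no drop-out | 168 / 201 | 0.84 | 6.9% |
| 42, 48 | Null, η = 0.0079 | 187 / 197 | 0.95 | 6.0% |
| 42, 48 | Planned OS effect, η = 0.0079 | 172 / 183 | 0.94 | 6.1% |
| 42, 48 | Planned OS effect, no drop-out | 187 / 201 | 0.93 | 6.2% |

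Strictly, a type I error belongs to the null rows. The planned-effect rows use the fraction the sponsor would project from its own 183 deaths.

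**Step 4: simulation.** In 40,000 simulated null trials (median 10.6 months, η = 0.0079), each look alone rejected in 5.0%. Either of months 36 and 48 rejected in 6.7%, and either of months 42 and 48 in 6.0%. Two independent tests would give 1 − 0.95² = 9.75%; the overlap in deaths keeps the figure well below that.

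**Step 5: levels that restore 5% at t = 0.85.** With the O'Brien-Fleming shape the critical values are c/√t and c. Solving for 5% gives c = 2.026 and a first-look value of 2.197, which are nominal levels of about 0.028 and 0.043. Equal levels at both looks would be about 0.036.

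**The case against.** **The first OS test is implied, not named.** No sentence says that OS is tested at the PFS cut-off. This stands as a caveat. Still, SAP 4.2 exempts nothing, the OS test sits among the efficacy analyses, and calling the later results final and added implies earlier ones.

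**OS has no stated alpha.** This also stands. A reader might infer that the plan sets OS at 0.05 twice and so states a wrong level. It does not: the level comes only by analogy with PFS, and no passage says significance at either look will be claimed.

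**The later result is already the definitive one.** SAP 4.2 calls it final, and the only OS event projection belongs to the 24-month follow-up. Read that way the level is 5%. This is the natural reading, but the plan does not say that the earlier p-value carries no inference.

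**OS is one of many unadjusted secondary endpoints in a phase II trial.** True. Settling this point does not make OS a controlled endpoint, which limits its weight.

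**Two stronger readings are not supported.** A reader might combine the at-least wording with protocol 14.5.1, where study end requires that "a relevant number of deaths have occurred to obtain information on overall survival", and infer an open-ended OS cut-off with a third look. But 14.5.1 defines the end of the study, SAP 4.2 plans the OS analysis at 24 months, and no later look is planned. A reader might also treat the first OS result as a harmful unblinding. The trial is open-label, no stopping decision is tied to that result, and recruitment has by then been closed for at least 12 months.

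**Conclusion.** The point holds in a limited form. As written, OS is analysed twice with the same test, and the documents neither split alpha nor make the first analysis descriptive. The type I error for OS is about 6.6 to 6.9% with looks at months 36 and 48, and about 6.0 to 6.2% if the main analysis moves to month 42. These figures rest on three conditions: the first OS test is actually run, both tests are read at two-sided 0.05, and significance at either look is claimed. They also assume exponential survival and uniform accrual. If only the later test counts, the level is 5%.

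The excess is therefore about 1 to 2 percentage points on a secondary endpoint, with no effect on the primary PFS test. It is worth correcting because the correction is nearly free and has to be made before OS by arm is known.

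**What to change.** 1. In SAP 4.2 and 9.2.4, state that the log-rank test at the cut-off 24 months after the last randomization is the only inferential OS test. At the main analysis, report OS descriptively: Kaplan-Meier curves, number of deaths, and hazard ratio with confidence interval, with no p-value and no OS claim.
2. If an OS test at the main analysis is wanted, prespecify O'Brien-Fleming-type levels, about 0.028 and 0.043 at an information fraction of 0.85, recomputed if the fraction differs.
3. Reconcile the maximum of 24 months (protocol synopsis and 7.1.1, SAP 3.1) with the at-least wording (protocol 13.2, SAP 5), so that the OS data cut-off matches the 24 months in SAP 4.2.

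The cost is a few sentences. No patient, visit or event count changes. Under option 1 no OS p-value is available at the main analysis; under option 2 the final OS test is run at about 0.043 instead of 0.05.
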